# 13.4.3 Interim and Final Analysis for Primary Endpoint

A single planned interim analysis of the primary endpoint for efficacy will be performed on the first 96 patients in the full analysis set who have completed the 3-month post-radiation therapy study procedures or withdrew from the study prior to completing the 3-month post-radiation therapy study procedures. The O'Brien-Fleming method will be used to control the Type I error rate and account for multiplicity and was chosen because it makes the early test at the interim analysis very conservative; the adjusted two-sided significance levels at the interim and final analysis are 0.003 and 0.049, respectively. The study may be suspended and terminated at the time of the interim analysis if the two-tailed p-value falls below 0.003. The final analysis of the primary endpoint will be performed on the first 192 assessable patients for efficacy. The interim and final analysis boundaries were generated using the PASS 15 power analysis and sample size software (2017).

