Based on the aforementioned single-institution study, the distribution of the combined patient-and provider-completed mRISRAS scores (averaged over the post-randomization assessments) were positively skewed. As such, we propose using the AUC to summarize the sequence of repeated patient-completed mRISRAS scores for each patient. This summary measure tends to be approximately normally distributed. We hypothesize that the Mepitel Film arm will be associated with an improved AUC summary measure, corresponding to decreased patient-completed mRISRAS scores compared with institutional standard of care. With 192 patients randomized in a 2:1 ratio (128 Mepitel Film; 64 existing institutional standard of care), the study will have at least 90% power for a two-sample t-test to detect an effect size of -0.5 (Mepitel Film vs institutional standard of care) based on the AUC summary measure with a two-tailed alternative and a 5% Type I error rate. These results assume that two sequential tests are made using the O'Brien-Fleming spending function (see Section 13.4.3).

We anticipate that up to 10% of patients will not have met the eligibility criteria and/or not have submitted any mRISRAS data, and thus the target sample size will be inflated to 216 patients (144 Mepitel Film; 72 existing institutional standard of care). Importantly, any placement of the Mepitel Film will make the patient evaluable for the primary analysis provided that the patient had at least one patient-completed mRISRAS score, and was randomized (See Section 13.4.2 and the definition of the full analysis set).

Using conservative estimates, based on the Alliance Community Interest and Feasibility Survey conducted in May of 2018, we anticipate an accrual rate of 9 patients per month; therefore, to achieve the targeted accrual of 216 patients we anticipate that the accrual period will be approximately 24 months. Since the last protocol scheduled follow-up visit is 60 months post-radiation therapy, the corresponding total study duration will be approximately 84 months.

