# 13.4.2 Analysis Plan for Primary Endpoint

The primary analysis will be based on the full analysis set, defined as all patients who were randomized and had at least one patient-completed mRISRAS score; furthermore, these patients will be analyzed in the arms to which they were randomized. Omitting patients from the primary analysis who do not provide any patient-completed mRISRAS data is not anticipated to cause any bias. The fact that patients do not provide any patient-completed mRISRAS data should be unrelated to the interventions to which patients were assigned. Furthermore, including a patient who does not provide any patient-completed mRISRAS data is not meaningful for analysis because the patient will not have a relevant contribution to the patient-reported outcome (PRO) estimate . Nonetheless, any potential bias arising from the exclusion of randomized patients who do not provide any patient-completed mRISRAS data will be fully investigated (see Section 13.7)

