In order to adjust for the stratification factors in the primary analysis, the AUC will be computed for the prophylactic arms based on estimated parameters from a repeatedmeasures (means) mixed model. The outcome measures used in the repeated-measures (means) mixed model are the serially measured patient- completed mRISRAS scores obtained at baseline (i.e, prior to the start of radiation), weekly during radiation therapy, at  $10 (\pm 4)$  days post-radiation therapy, and at 3-months post-radiation therapy. The covariates included in the model are indicator variables for all assessment time points, an indicator for the prophylactic method, the corresponding interaction terms, and the four stratification factors. This analytic approach, which is a likelihood method, to compare the prevention of radiation-induced dermatitis between the two prophylactic methods will preserve the full analysis set, allow for missing data (i.e. under the reasonable assumption of missing at random), and account for important covariates. Furthermore, it has been shown that this analytic approach is superior to a simple AUC summary measure in terms of both bias and precision.  Because of the gains in precision, the power analysis described in Section 13.3 is conservative; i.e. the power associated with the repeated-measures (means) mixed model will be greater since the addition of all available patient-completed mRISRAS scores will provide more information. We will report the summary statistic AUC for each arm, including the respective 95% confidence intervals, as well as the difference in AUC between the two arms along with the 95% confidence interval for the true, but unknown difference; the difference in AUC between arms will be estimated from the repeatedmeasures (means) mixed model and contrast for the summary statistic AUC. Further the two-sided *P*-value testing the null hypothesis of no difference  $(H_0: \mu_{AUC_1} = \mu_{AUC_0})$  versus the two-sided alternative hypothesis that there is a difference  $(H_a: \mu_{AUC_1} \neq \mu_{AUC_0})$  will be obtained from the repeated-measures (means) mixed model. Provided that the difference in AUC achieves statistical significance at the 5% level, the primary objective will have been met.

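### Sections 13.4.2 and 13.4.3 define different populations for the same primary test: every randomized patient with a score, or only the first 192 assessable patients

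*Combined protocol and SAP*

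**What the plan says.** All references are to the combined protocol and SAP.

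- **Section 13.4.2** bases the primary analysis on the "full analysis set, defined as all patients who were randomized and had at least one patient-completed mRISRAS score", analysed as randomized and with no limit on number. It adds that the likelihood-based comparison "between the two prophylactic methods will preserve the full analysis set, allow for missing data".
- **Section 13.4.3** states for the same endpoint: "The final analysis of the primary endpoint will be performed on the first 192 assessable patients for efficacy". The word *assessable* is not defined there. The interim analysis is to be "performed on the first 96 patients in the full analysis set who have completed the 3-month post-radiation therapy study procedures"; patients who left the study before that point also count. The two-sided levels are 0.003 at the interim and 0.049 at the end.
- **Section 13.3** powers the trial on 192 patients (128 and 64), then allows for loss: "We anticipate that up to 10% of patients will not have met the eligibility criteria and/or not have submitted any mRISRAS data", so "the target sample size will be inflated to 216 patients" (144 and 72). It also says that "any placement of the Mepitel Film will make the patient evaluable for the primary analysis", provided the patient was randomized and gave at least one score.
- **Section 13.3** further allows accrual beyond 216, restricted to African American and Hispanic women, until 54 have been enrolled.
- **Section 13.4.4** removes ineligible patients only in the per-protocol sensitivity analysis, so ineligible patients with data stay in the full analysis set.

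**The concern.** Two statisticians working from this document could build different data sets for the primary test. One would follow 13.4.2 and take everyone randomized with a score. The other would follow 13.4.3 and stop at 192. A choice left open in this way could be settled after data have been seen, and the primary result also decides whether the gatekept secondary family in 13.5.2 is tested at all.

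The cap also leaves out randomized patients who supplied primary-endpoint data, which departs from the plan's own definition of its main analysis set. Extension patients, who are selected by race or ethnicity, raise the same question: the plan does not say whether they enter the primary test.

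**Working it through.** **Inputs.** Powered size 192 at 2:1, effect size 0.5, two-sided 5%, target accrual 216, loss up to 10%, accrual 9 per month (all 13.3). Interim at 96 patients, levels 0.003 and 0.049 (13.4.3).

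**1. The plan's own figures.**
- For a two-sample t-test with 128 and 64 patients, noncentrality is 0.5 / sqrt(1/128 + 1/64) = 3.27. Single-look power at two-sided 0.05 is 0.901.
- With one interim at 96/192 = 0.50 and Lan-DeMets O'Brien-Fleming spending, the levels come out at 0.00305 and 0.0490, with two-look power of 0.903.
- Inflation: 192 / 0.90 = 213.3, or 214. By arm, 64 / 0.90 = 71.1, rounded up to 72, and twice that is 144, total 216.

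The stated design therefore reproduces.

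**2. How many patients the cap leaves out.**
- All of the 10% lack data: 216 x 0.90 = 194.4, and 194.4 - 192 = 2.4, about 2.
- Nobody lacks data: 216 - 192 = 24.

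The 10% combines ineligible patients, who remain in the full analysis set, with patients who gave no score. It is not split, so neither end is favoured. Extension patients would add to the number, but the table in 13.9 expects 35 + 19 = 54 such women within the 216, so the extension is a contingency.

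**3. Precision.** Relative interval width is sqrt(N/192):
- N = 194.4: 1.006, so the capped interval is 0.6% wider.
- N = 216: 1.061, so it is 6.1% wider.

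**4. Power at effect size 0.5** (noncentral t, single look, two-sided 0.05):

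| Patients analysed | Power |
|---|---|
| 192 | 0.901 |
| 194.4 | 0.905 |
| 216 | 0.932 |

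**5. Final level if more than 192 are analysed.** Take the two test statistics as bivariate normal with correlation sqrt(96/N), fix the interim at 0.003, and solve for the final level that gives overall two-sided alpha of 0.0500:

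| N | Information at interim | Overall alpha with final 0.049 | Final level for 0.0500 |
|---|---|---|---|
| 192 | 0.500 | 0.0500 | 0.0490 |
| 194.4 | 0.494 | 0.0500 | 0.0490 |
| 216 | 0.444 | 0.0502 | 0.0488 |

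Two-look power at 216 is 0.9330 with 0.049 and 0.9328 with 0.0488, a loss of 0.0002.

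**6. Timing.** The 192nd patient with data is randomized at month 192/9 = 21.3 with no loss, or 192/(9 x 0.9) = 23.7 with 10% loss. The 216th is randomized at month 216/9 = 24.0. Waiting for 216 adds 2.7 or 0.3 months.

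**The case against.** The best defence is that the cap is deliberate. The trial is sized at 192, 216 exists only to protect that number, and 96 is exactly half of 192. Stopping at 192 keeps the information fraction at 0.50, where 0.003 and 0.049 give an overall alpha of 0.0500. Defining *assessable* and *first* in one clause would then settle the matter without touching the boundaries. This is coherent, and the cap does have that merit. But over-enrolling as a buffer does not explain leaving randomized patients with data out of a set defined as all of them, and 13.4.2 would still need to be amended to admit the cap.

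A second defence is that 192 is only a timing trigger. That may have been the intention, but the sentence says the analysis is performed on those patients, and the parallel interim sentence plainly defines a data set. A third is that *assessable* simply means membership of the full analysis set. That is the natural reading, and the two sections still differ in number.

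Several stronger readings are tempting but not supported:
- **That later patients have no planned use.** This is true only of the primary test. The per-protocol set (13.4.4), the safety population (13.5.2) and the analyses of African American and Hispanic women (13.9) are not capped.
- **That Type I error is inflated, because 13.4.2 declares success at 5%.** Taken literally after a 0.003 interim, a final 5% would give 0.0510 to 0.0512. But 13.3 and 13.5.2 use 5% as the overall rate, and 13.4.3 states the adjusted 0.049 for the final test.
- **That the cap biases the comparison through early withdrawals.** This would need an ordering rule for the final set and withdrawal rates that the documents do not give.
- **That 192 is a leftover from before the inflation.** The document uses 192 as shorthand for the powered number, and nothing shows how the sentence came about.

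**Conclusion.** The contradiction is real and concerns the analysis set for the primary test, so it should be fixed. Its numerical effect is modest: about 2 to 24 randomized patients with data left out, an interval 0.6% to 6.1% wider, and power that meets the 90% target under either rule. Type I error is sound with the cap and remains sound without it once the final level is recomputed.

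These figures assume that exactly 216 are accrued in a 2:1 ratio, that loss stays within the planned 10%, and that information is proportional to the number of patients. Extension patients would raise the number left out above 24.

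The gain from the change is some precision, a primary set that matches randomization, and a single data set fixed in advance.

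**What to change.** - **Section 13.4.3.** State that the final analysis includes all full-analysis-set patients among the first 216 randomized, once each has completed the 3-month visit or withdrawn before it, and that 192 is the planning minimum. State that patients from the minority accrual extension are added only in a pre-specified supplementary analysis, so the primary readout does not wait for them.
- **Final level.** Compute it from the 0.003 spent at the interim and the actual information fraction: 0.0490 at 192 to 194 patients, 0.0488 at 216.
- **Section 13.4.2.** Replace the 5% success criterion with a reference to the final level in 13.4.3. This is a clarification of wording only.

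**Cost.** No new patients or data are needed. At planned accrual the readout comes about 0.3 to 2.7 months later, and the lower threshold at 216 costs about 0.0002 of power. The interim would fall at 44% to 49% of the information and not at 50%. The 0.003 then becomes a fixed amount of alpha spent and is no longer the exact O'Brien-Fleming value; at 44%, a Lan-DeMets O'Brien-Fleming function would spend about 0.0015. Overall alpha is still held at 0.05, but the section should say that the interim level is fixed at 0.003.

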# 13.4.4 Planned Sensitivity Analyses for Primary Endpoint

Recognizing that a number of additional variables may confound the interpretation of the results from the primary analysis, a sensitivity analysis is planned at the time of the final analysis to assess the robustness of the primary results in the presence of potential confounding variables such as reconstructed breast size, separation, and modality of boost. Further sensitivity analyses for the primary endpoint at the time of the final analysis will comprise subgroup analyses to ascertain whether the effect of Mepitel Film remains clinically robust according to various categories of topical products (e.g. aqueous creams, petroleum ointments, etc.) used on the existing institutional standard of care arm.

The study will be conducted at multiple sites. To account for within-site homogeneity in the primary endpoint, we will repeat the primary analysis and include a site-level random effect in the model.

Additionally, the primary analysis will be repeated on the per-protocol analysis set, defined as all patients in the full analysis set who were deemed eligible.

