### 1.0 BACKGROUND

### 1.1 Introduction

Radiation therapy is an integral part of breast cancer treatment for many women and is associated with a unique toxicity profile. In recent years, technological improvements in radiation delivery systems have resulted in reduced doses to normal tissues. However, in women requiring post-mastectomy radiotherapy (PMRT), decreasing radiation dose delivered to the skin may not be desirable because the skin is considered part of the treatment target. Indeed, in PMRT the skin is often intentionally covered with bolus to ensure coverage of the dermis and dermal lymphatics. Amongst women undergoing PMRT, radiation dermatitis continues to be a widespread source of treatment-related morbidity.2 Acutely, radiation dermatitis manifests as moist desquamation in up to 73% of patients, grade 3+ pain in up to 32% of patients, pruritus, and nearly universal erythema. The acute skin reaction may compromise quality of life. Importantly, the acute toxicity of radiation dermatitis is correlated with the risk of long term sequelae. Severe acute toxicity may lead to consequential chronic effects including telangiectasias, hyperpigmentation, and, in extreme cases, ulceration and necrosis.  Severe skin toxicity may also lead to incomplete or interrupted treatment, which risks compromise of the oncologic outcomes, and could increase the risk of breast reconstructive complications, including reconstruction failure. 9,10 The etiology of radiation dermatitis is incompletely understood. There is wide variation in the severity of dermatitis between patients. suggesting that the etiology of severe radiation dermatitis is more complex than the dose to the skin or the volume of skin irradiated alone. Given the potential impact on treatment related morbidity and quality of life, a better understanding of the pathogenesis of radiation dermatitis and means of preventing this important complication of PMRT is needed.

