### 1.2 Previous studies for the prevention of radiation dermatitis

Over the years, multiple topical agents have been investigated for the prevention of radiation dermatitis, with mixed, but largely negative outcomes. Over fifty studies have reported between 1979 and 2017 examining various topical agents. 11 Despite clinical interest, most agents have not been consistently advantageous. Topical steroids have been evaluated in trials consisting mostly of whole breast radiation patients and have shown some modest efficacy. In one such trial, while improvements were noted in certain patient reported measures, there was no difference in the primary endpoint of mean maximum grade of radiation dermatitis. 12 A second randomized study, largely performed in the setting of hypofractionated whole breast radiation, demonstrated a significant reduction in radiation dermatitis, as measured by reflectance spectrophotometry, and statistical improvements in quality of life with mometasone, when compared to Diprobase. However, the absolute improvement was small, with a reduction in average erythema mean score from 1.45 to 1.3, leading to some question about the clinical relevance of the reductions. A recent trial amongst women undergoing PMRT found that compared with eucerin cream, 0.1% mometasone resulted in decreased rates of moist desquamation from 66.7% to 43.8% and longer time to development of grade 3 dermatitis; however, there was no difference in patient reported outcomes. Thus, while corticosteroids appear to show some impact on development of high grade dermatitis, impact on quality of life in the highest risk population is unclear, and preventive use of mometasone has not been widely adopted.

Multiple non-steroidal topical creams have been examined, with no clear improvement in dermatitis prevention. Compared with standard of care, hyaluronic acid based gel was worse than a petroleum based gel at prevention of grade 2 or higher dermatitis.  The twice daily application of processed ultra emu oil was also examined in a double- blind, placebo-controlled pilot study; however, no differences were noted in the primary endpoint examining radiation

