#### 13.0 STATISTICAL CONSIDERATIONS

# 13.1 Study Design

This is a randomized, controlled clinical trial to determine the ability of Mepitel Film to reduce the severity of radiation dermatitis in patients undergoing post-mastectomy radiotherapy for breast cancer when compared with the existing institutional standard of care. Patients will be randomized in a 2:1 ratio to receive either Mepitel Film or the existing institutional standard of care. The 2:1 randomization favoring Mepitel Film was chosen to aid in recruitment given an expected enthusiasm for Mepitel Film based on previously published series. Randomization will be stratified on the basis of a breast reconstruction (yes; no), planned boost (yes; no), planned bolus (yes; no), and according to 3 levels of BMI, consistent with the established cut-offs as defined by the WHO (< 25; 25-29.99; and  $\ge 30$ ).

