# 13.3 Sample Size, Accrual Time, and Study Duration

Our statistical plan is informed by the largest single-institution, randomized, intra-patient-controlled study of Mepitel Film to date. This trial evaluated 78 patients receiving radiation therapy for breast cancer in which all patients had a portion of skin in the treatment field covered by Mepitel Film. Based on the combined patient- and provider-completed mRISRAS scores, utilization of Mepitel Film demonstrated a substantial 92% reduction in the extent of radiation-induced skin reactions, compared to an adjacent area of skin treated with aqueous cream. 42 The

findings translated into a large (> 0.80) effect size providing a benchmark used to guide our study's power analysis. The prophylactic effect was more marked, when based solely on the patient-completed mRISRAS scores. We expect the effect size will be attenuated given the multi-institutional nature of our study and due to the anticipated heterogeneity in the use of skin care products within our existing institutional standard of care arm, corresponding to a medium effect size of 0.5. An effect size of 0.5 is considered clinically relevant for our patient population receiving radiation therapy, and who are at risk for acute radiation dermatitis, which may compromise quality of life. Further, such an effect size has also been suggested to be clinically significant in general for patient-reported quality of life outcomes in cancer populations.

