#### 13.5.3 Planned Sensitivity Analyses for Secondary Endpoints

As a supportive analysis for the first secondary endpoint (centralized, blinded provider-completed mRISRAS scores), the van Elteren statistic, which is an extension to the Wilcoxon rank-sum test that accounts for the stratification factors, will be calculated.

A sensitivity analysis is planned for the second and third secondary endpoints in order to assess the robustness of the results in the presence of potential confounding variables such as reconstructed breast size, separation, and modality of boost. Further sensitivity analyses for the second and third secondary endpoints will comprise subgroup analyses to ascertain whether the effect of Mepitel Film remains clinically robust according to various categories of topical products (e.g. aqueous creams, petroleum ointments, etc.) used on the existing institutional standard of care arm.

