#### APPENDIX III PHOTOGRAPHY STANDARD BREAST PROTOCOL

# Standard Breast Protocol - Arms at side for first view

#### Alliance A221803

#### APPENDIX IV SKIN CARE FORM

Please record all skin care products patient is currently applying to treatment area (circle all that apply)

- a. Aqueous cream (i.e. Vanicream, Eucerin, etc.)
- b. Petroleum based ointments (Aquaphor, Vaseline, etc.)
- c. Aloe Vera
- d. Vinegar soaks
- e. Prescription creams/ointments (i.e. mometasone, lidocaine, topical antibiotics)
- f. Wound care products (i.e xeroform gauze, silvadene, etc.)

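### The product-category subgroup analyses in 13.4.4 and 13.5.3 sort only the controls, by products recorded after randomization; they should be labelled descriptive and non-randomized, not used to judge robustness

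*Combined protocol and SAP*

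**What the plan says.** Section 13.4.4 lists subgroup analyses among the sensitivity analyses for the primary endpoint. Their purpose is to see whether the film effect stays robust across "various categories of topical products (e.g. aqueous creams, petroleum ointments, etc.) used on the existing institutional standard of care arm". Section 13.5.3 adds: "Further sensitivity analyses for the second and third secondary endpoints will comprise subgroup analyses", with the same purpose and the same categories. The blinded photograph endpoint is not included.

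Neither section says how a control is assigned to a category, at which visit, what happens when several products are used, or which film patients are the comparator.

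Product use is captured on the Appendix IV form: "Please record all skin care products patient is currently applying to treatment area (circle all that apply". One of its categories is "Prescription creams/ointments (i.e. mometasone, lidocaine, topical antibiotics". The Study Calendar (5.0) schedules the form weekly during radiation, at 7-14 days and at later visits. Section 7.2.1 leaves control-arm care to the treating physician and makes the Appendix IX guidance optional. Section 8.1.2 bars film patients from putting these products over the film.

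Section 13.3 gives "anticipated heterogeneity in the use of skin care products within our existing institutional standard of care arm" as one reason for assuming an effect size of 0.5. In 13.1, randomization is stratified by reconstruction, "planned boost (yes; no), planned bolus (yes; no), and according to 3 levels of BMI". Neither site nor skin-care product is a factor.

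**The concern.** A subgroup contrast keeps the protection of randomization only if both arms are split by something fixed independently of assignment and outcome. Here only the controls are split, and apparently by what they applied during treatment.

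Appendix IX ties several product classes to the skin's response: petroleum ointment once erythema shows, prescription topicals for discomfort, burning or itching, and wound care for a moist reaction. Where sites follow it, controls who react badly move into some classes and controls who do well stay in others. The film would then look better against symptom-driven products and worse against moisturizer alone, even if its effect were the same for everyone.

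Because product heterogeneity is one of the plan's reasons for its effect size, readers will look to these analyses to learn whether the film beats particular products. They could take a sorting artefact for a real difference between product classes.

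**Working it through.** **How directly product class is linked to the endpoints.** The primary endpoint (13.4.1) uses only the four patient items in Appendix VI: tenderness, discomfort or pain; itch; burning; and effect on daily activities. Erythema and moist desquamation are provider items.

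| Appendix IX product | Trigger | Where the trigger is scored |
|---|---|---|
| Aqueous cream | None; for moisture | Not applicable |
| Petroleum ointment | Visible erythema | Provider scale |
| Prescription topicals | Discomfort, burning, itching | Patient scale |
| Wound care | Moist reaction | Provider scale |

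The link is therefore most direct for 13.5.3 (provider and combined scores) and, within 13.4.4, for prescription topicals.

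**The plan's own figure.** With 128 film and 64 control patients and effect size 0.5 (13.3), SE = sqrt(1/128 + 1/64) = 0.153. Then 0.5/0.153 = 3.27, and power = Phi(3.27 - 1.96) = about 90%, as stated. Nothing below changes it.

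**Illustration of size.** The documents give no correlation between product choice and outcome, so these inputs are assumptions:
- A latent product-choice variable correlates r with the control's outcome, with r = 0, 0.3 or 0.5. The correlation of the observed yes/no class is lower, r*phi(t)/sqrt(p(1-p)). At p = 0.438 that is 0.794r, or 0.24 and 0.40.
- The share p of controls in the class tracks reaction rates quoted in the protocol: "moist desquamation in up to 73% of patients, grade 3+ pain in up to 32% of patients, pruritus, and nearly universal erythema" (1.1), and, in one post-mastectomy trial, "decreased rates of moist desquamation from 66.7% to 43.8" per cent (1.2). I use 43.8% and 73%. This is plausible only where sites follow Appendix IX.
- The products themselves do not change symptoms.
- The true film effect is -0.5 SD in everyone, and the comparator is the whole film arm.

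With t = z(1-p), the user mean is shifted up by r*phi(t)/p and the mean of the rest down by r*phi(t)/(1-p). The multipliers of r for users and rest are:
- p = 0.438: 0.900 and 0.701
- p = 0.73: 0.453 and 1.225
- p = 0.90: 0.195 and 1.755

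The false gap is r times their sum. Its sampling 95% half-width is 1.96*sqrt(1/users + 1/rest), because the film arm cancels.

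| p | Users / rest | Film vs users (r = 0 / 0.3 / 0.5) | Film vs rest (r = 0 / 0.3 / 0.5) | False gap (r = 0 / 0.3 / 0.5) | Half-width |
|---|---|---|---|---|---|
| 43.8% | 28 / 36 | -0.50 / -0.77 / -0.95 | -0.50 / -0.29 / -0.15 | 0 / 0.48 / 0.80 | 0.49 |
| 73% | 47 / 17 | -0.50 / -0.64 / -0.73 | -0.50 / -0.13 / +0.11 | 0 / 0.50 / 0.84 | 0.55 |

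For a product used by an assumed 90% of controls, the bias against users is only 0.3 x 0.195 = 0.06 to 0.5 x 0.195 = 0.10 SD. The rest is about 6 patients, whose contrast with 128 film patients has half-width 1.96*sqrt(1/128 + 1/6) = 0.82 SD, too wide to be useful.

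**Check.** In 20,000 simulated trials at r = 0.5 the mean contrasts were -0.943 and -0.153 (28/36), and -0.718 and +0.110 (47/17). This confirms the arithmetic under the assumed model. It does not show that the bias exists in this trial.

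**The case against.** The strongest reply is that the plan leaves the rule open rather than choosing a biased one. A grouping by site practice also fits the wording, and 7.2.1 does describe care as varying between institutions. That stands as a condition on the point. But the text speaks of products used, the only product data described are the Skin Care Form entries, and I found no site-level product field in the documents. The week-1 form, if completed before the first fraction, would avoid reaction-driven sorting, but it is still post-randomization and gives no film comparator.

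The analyses also carry no alpha, no stated test and no place in the gatekeeping. That is correct, and it limits the consequence to interpretation. Even so, they are called sensitivity analyses meant to establish robustness, whereas 13.9 says its race/ethnicity and socioeconomic differences are evaluated descriptively.

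The illustration is open to three fair criticisms:
- The class shares borrow moist-desquamation rates, so they fit wound care. The categories 13.4.4 names as examples are aqueous creams and petroleum ointments. Aqueous cream has no reaction trigger, and the bias against users of a near-universal product is small.
- Provider-observed reactions may track patient scores loosely. The mometasone trial in 1.2 lowered moist desquamation without a patient-reported difference, and in Appendix I, 8 of 9 patients reporting severe or very severe burns were graded 1-2. An r of 0.3 to 0.5 for the primary endpoint is therefore unsupported by data.
- At r = 0.3 the false gap (0.48 to 0.50) lies just inside the sampling half-width (0.49 to 0.55). Only the higher assumption clearly exceeds it.

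Finally, that the form has no field for why a product is used rests on Appendix IV as printed. The electronic case report forms are not in the documents.

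**Conclusion.** The point holds as a minor one. If controls are classed by products actually used, film against a product-defined slice of controls is not a randomized comparison and cannot show that the effect is, or is not, robust by product. The size is unknown. The 0.48 to 0.84 SD gap depends on the assumed r and class share; it goes to zero where product choice follows site or physician habit.

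Three stronger readings are tempting and not supported:
- That the primary result or type I error is at risk. The primary analysis compares the arms as randomized, and these subgroups sit outside the testing sequence. Other checks also exist: covariate adjustment, a site random effect, a per-protocol set, a longitudinal model and imputation (13.4.4, 13.4.5, 13.7).
- That every product category is distorted to the illustrated extent. Appendix IX is optional, aqueous cream is not reaction-driven, and only prescription topicals have triggers that are patient items.
- That the sponsor has committed to a biased analysis. The rule is unstated; the conclusion follows from the natural reading, not from an explicit rule.

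**What to change.** In 13.4.4 and 13.5.3:
- State how controls are classed (source form, visit or window, and handling of several products) and that the whole film arm is the comparator.
- State that results by products actually used are descriptive and non-randomized, are reported as estimates with 95% confidence intervals, and will not be used to conclude that the film effect is or is not robust by product.
- Tabulate product use by arm and visit.

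This takes two or three sentences and needs no new data. Sample size, power, alpha, gatekeeping and patient care do not change. The real cost is that the trial gives up the planned robustness claim by product.

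Grouping both arms by each site's usual practice could be added as an exploratory analysis, but it is not part of the fix. Classes would be coarse and, for open sites, declared retrospectively. They would be confounded with other site features and not balanced by design. Precision would be low: with two equal classes (64 vs 32 in each) the interaction has a 95% half-width of 1.96*sqrt(2*(1/64 + 1/32)) = 0.60 SD.
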